Primary Endpoint Secondary Endpoints	
The primary endpoint of this study will be good handwashing practice defined as students who wash their hands with water and soap before eating assessed by structured handwashing observations.
 
The secondary endpoints are:
 
 Good handwashing practice defined as students who wash their hands with water and soap after using the toilet assessed by structured handwashing observation Self-reported handwashing practice answered for two critical events; before eating and after using the toilet, on a Likert scale ranging from almost never to almost always. The well-being of students assessed by KINDL tool Number of total coliforms and E.coli colony-forming units (CFUs) per hand before handwashing. Hygiene-related health outcomes and absenteeism incidence. The health outcomes will be reassessed with local experts in the country to assure feasibility before the start of the intervention.
Study Design	
Overall project: Multi-center cluster-randomized controlled trial (cRCT) design.
 
Module 1-3 will be repeated three times within the cRCT at baseline, three months post-intervention and at endline. Module 4 data collection will take place in both study arms longitudinally starting after the intervention has been implemented. Module 5 will be a self-reported survey administered for the parents of the students included in the study at baseline in Palestine. Module 6 and 7 are qualitative focus group discussions (FGDs) and interviews and will take place after the second round of data collection in Modules 1-3.

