
Measurements and Procedures
	
Different methods across modules will be used to achieve the objectives of this project. These modules will include qualitative and quantitative data approaches in order to enable a triangulation of the overall project results. The following modules will be used in the cRCT and the overall project: (i) Module 1: A combined RANAS and wellbeing survey, (ii) Module 2: Structured handwashing observations, (iii) Module 3: Microbiological analysis of hand rinse samples, (iv) Module 4: Diary approach for pre-defined health outcomes and absenteeism incidence, (v) Module 5: personal, physical, and social contextual factor survey, (vi) Module 6:FGDs and (vii) Module 7: Key informant interviews (KII).
 
Endpoints of Modules 1-3 will be assessed at baseline, at follow-up and endline of the cRCT. Module 4 will be used to collect data longitudinally over the course of 12 months. Module 5 will be assessed at baseline and only in Palestine, Module 6 and 7 will be used in the middle of the intervention phase in the intervention groups.

Number of Participants with Rationale (if no Power Analysis conducted)
	
The sample size calculation yielded that 13 schools are needed per arm with 50 students per school. With political instability and other factors which might lead to a loss of follow-up, we have 7 schools as backup schools. This will lead to 26 schools in total with a total number of 1300 students. The number of students participating in different modules will differ due to the capacity limitation of assessing the 50 students included in each school. For module 1, only 25 students of the 50 students included in the study in each school. For module 2, the 50 students included in the study in each school will be targeted for assessment using this module. For Module 3, 12 students out of the 25 randomly selected students to be targeted with RANAS and well-being survey will be targeted for assessment using this module.

	
Module 4 follows the sample size calculation of the cRCT design, hence 50 students from each of the 26 schools will be monitored. For Module 5, all students in the included classes in each school in Palestine will be delivered a survey to be self-reported by their parents. For Module 6, 10 FGDs (including students) and 5 FGDs (including teachers) will be administered and for Module 7, 10-20 interviews.

Study Duration	14 months

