2.1.1 Access to water and hygiene for disease prevention

Studies have shown that proper handwashing with soap reduces the transmission of diarrheal diseases by 30% to 48% (Bloomfield *et al.* 2007; Ejemot *et al.* 2008; Freeman *et al.* 2014; Prüss-Ustün *et al.* 2019) and respiratory diseases by 21% (Aiello *et al.* 2008; Warren-Gash *et al.* 2013). Furthermore, proper hand hygiene plays an important role in controlling the spread of epidemics such as cholera (Taylor *et al.* 2015; Ngwa *et al.* 2020), ebola (Wolfe *et al.* 2017), hepatitis E (Teshale *et al.* 2010), SARS (Fung and Cairncross 2006), and shigellosis (Khan 1982). Also, during the current COVID-19 pandemic, handwashing with soap has received unprecedented attention for being the most effective measure to reduce the transmission of the infection. For example, Beale *et al.* (2021) showed that improved hand hygiene reduced the likelihood of contracting a COVID-19 infection by 36% (Beale *et al.* 2021). Indeed, if there is anything that the COVID-19 pandemic has reinforced, it is that increasing access to sustainable sanitation and handwashing facilities is more important than ever.

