2.3 The hands4health project

This project is funded by the Swiss Development Cooperation (SDC) (<https://hands4health.dev/>) and aims to increase hygiene in schools without any direct access to water in the context of humanitarian crises. The project has a strong focus on the Sustainable Development Goal (SDG) 6, clean water and sanitation. In addition, the SDG 1 (no poverty), SDG 3 (good health and wellbeing), SDG 4 (quality education), SDG 5 (gender equality), SDG 10 (reduced inequalities), and SDG 11 (sustainable cities and communities) are targeted (Pradhan *et al.* 2017). The project is led by 10 partners from academia, non-governmental organizations (NGOs), and the private sector. To increase the level of hygiene, an intervention package consisting of (i) a handwashing station called Gravit'ea (only in Nigeria), (ii) rehabilitation of WASH infrastructure (only in Palestine) (iii) a behaviour change intervention from Ranas Ltd., a spin-off company of the Swiss Federal Institute of Aquatic Science and Technology (Eawag), (iv) training for monitoring residual chlorine in water storage by Fachhochschule Nordwestschweiz (FHNW) (only for Palestine), (v) capacity development on O&M and overall management by Fachhochschule Nordwestschweiz (FHNW), and (vi) the management of WASH infrastructure at facilities, including water storage, water distribution, handwashing and sanitation by FHNW. The Gravit'ea is designed by Gravit'ea Association, and evaluated by FHNW previously together with Gravit'ea and will be tested by the FHNW with filters supplied from the company Martin Systems. The Ecole Polytechnique Fédérale de Lausanne (EPFL) will test different greywater disinfection methods. The behavioural change intervention will be designed and lead by Ranas Ltd. The NGOs Terre des hommes (Tdh) and Cesvi will support the intervention and all data collection with local teams and expertise in Nigeria and Palestine, respectively. The Swiss Tropical and Public Health Institute (Swiss TPH) will lead the efficacy assessment of the project. The Palestinian Polytechnic University (PPU) and the University of Maiduguri (UNIMAID) have leading roles in the technology evaluation and user-centered design for local context; impact evaluation; water quality analysis, data collection and analysis; and quality control. Skat Foundation will coordinate the development of a systematic approach to facilitate handwashing in institutional settings, as well as develop an overall Theory of Change (ToC) for the intervention and a stakeholder engagement strategy. The ToC process, which will be continued throughout the project duration, and the systematic approach are directly related – both processes provide feedback to each other. One of the main results will be a Theory of Action (ToA), which will help the field and project teams to plan and implement their activities in a strategic and targeted way. The ToC aims to help local teams and the researchers to understand how the local WASH system works in schools in Nigeria and Palestine, and to identify the interplay of actors and factors that shape the overall system dynamic.

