4 STUDY DESIGN

The overall project will follow a multi-center cluster-randomized controlled trial (cRCT) design (Figure 2). Prior to this study, a group of schools in the study's target areas were surveyed by the Tdh (in Nigeria) and Cesvi (in Palestine) using the Facility Evaluation Tool for WASH in Schools ([FACET WINS](#)) which is a monitoring tool for WASH delivery services in schools. From these schools a subsample was identified which fulfils certain inclusion criteria (for the inclusion criteria see chapter 5.2 Inclusion criteria).

This subsample was handed over to the local Tdh and Cesvi collaborators who carefully assessed the security situation around the schools. The Tdh and Cesvi collaborators then selected 26 facilities per country, which are most probable to still be accessible for data collection within the next year. These 26 schools will then be allocated to the two arms (intervention vs. control) with covariate constrained stratified randomization using computer-generated randomization code provided by a statistician not involved in any field activities. The intervention arm will receive the full intervention package (handwashing station, behavioural change intervention, capacity development, and management support). The control arm will receive nothing for the duration of the intervention (12 months). Afterwards, they will receive the same intervention package with potential improvements identified in the former intervention group.

In the selected schools, 50 eligible students from each school will be selected from one or two classes within the age group (10-12 years) using random sampling. If the school has at least one class that has ≥ 50 students within the target age group, the sample will be selected from that class, otherwise, the sample can be selected from two classes. For module 1, only 25 students of the 50 students included in the study in each school will be involved. For module 2, the 50 students included in the study in each school will be targeted for assessment using this module. For Module 3, 12 students out of the 25 students targeted with assessment using module 1 will be targeted for assessment using this module.

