To assure the quality and functioning of the Gravit'eau handwashing stations, regular integrity tests and water quality tests will show if the systems are still functional and capable to remove the bacteria. *E.coli* tests of handwashing water will show if there is any recontamination or any integrity problem. In case there is a problem, we will provide an alternative solution (e.g. bucket with soap) and rehabilitate the handwashing systems or dose chlorine into handwashing systems and repeat the test.

In case a school has 25% higher negative health outcomes than the average of all schools, the regional Ministry of Education and Ministry of Health will be consulted to check if this is usual. If not, the study will have to be stopped in this school.

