6.2 Determination of sample size

The number of clusters (schools) and students per school was assessed by simulations using the software R aiming for a power of 80% at the 95% confidence level. The Intraclass Correlation Coefficient (ICC) was assumed at 0.2. The simulation assumed a prevalence of handwashing occurrence before eating during the time of observation (3 hours) taking place over one day of 20% in control vs 45% in intervention schools after 1 year from the baseline. Based on this assumption, 13 schools are needed per arm with 50 students per school. However, the number of students assessed for different modules will differ due to the capacity limitation of assessing the 50 students included in each school.

For Module 1, only 25 students randomly selected out of the 50 students randomly selected from the classes included in the intervention in each school will be targeted. For Modules 2 and 4 the 50

students randomly selected from the one or two classes included in the intervention in each school will be targeted. For Module 3 only 12 students randomly selected out of the 25 students involved in module 1 in each school will be targeted. For Module 5, all students in the the classes included in the intervention in each school will be invited to participate by delivering a survey to be reported by one of their parents. For Module 6, 10 gender-separated FGDs will take place in the included schools in the intervention arm; 5 FGDs for each gender. In addition, 5 FGDs targeting teachers will be conducted. For Module 7, 10-20 interviews will be conducted.

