9.2 Risk-benefit ratio

With the H4H intervention, the schools will receive much-needed handwashing infrastructure. An added benefit of Gravit'eau is that it only has to be refilled with water about once a month. This can save the school community precious time at work and water can be saved at the school level to be used as drinking or cleaning water. With the RANAS behaviour change program, the students will receive valuable information on how to maintain good hand hygiene during their stay inside and outside the school. This knowledge together with the available infrastructure will enable the students to better protect themselves against infections and enhance their well-being and satisfaction towards the handwashing structure in their schools. In addition, the students can transfer their knowledge to other students in the school or their families and communities. Finally, if the intervention helps to foster better hygiene at the school level, the school might become more attractive to students and offer a better learning experience.

The control schools will not receive any form of intervention during the year where the intervention package is being tested in the intervention schools. However, after this year, they will also receive an intervention package.

Depending on the Covid-19 situation in the study location, a slightly increased risk of infection arises during the FGDs. However, by conducting the FGDs outside with the use of masks and hand sanitizer and by distancing, this risk will be reduced to a minimum. In addition, the Gravit'eau does not contain water for drinking. Health effects of regular ingestion of Gravit'eau water have so far not been tested. By clearly introducing the Gravit'eau as a handwashing station and by clearly labelling the station with signs that signify "no drinking water", this risk will be reduced. During the piloting phase, the most appropriate and understandable signs will be chosen with the local staff.

To conclude, the benefits of this study for the participants, the schools, and the teachers clearly outweigh the potential risks for study participants. Moreover, the risk of contracting Covid-19 is already a daily risk for the school communities and might even be reduced through better access to handwashing stations.

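### The only illness-rate trigger compares each school with an average that includes the intervention schools, so a rise shared by the intervention arm is diluted

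*Combined protocol and SAP*

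**What the plan says.** Section 4.3 (Measures to minimize bias) sets the rule: "In case a school has 25% higher negative health outcomes than the average of all schools", the regional education and health ministries are consulted, and the study stops in that school if they do not find the level usual. The discontinuation lists in Sections 4.6 and 5.4 contain no other trigger based on illness rates. The quarterly look at the diary, also in Section 4.3, is made by school to check reporting quality.

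Schools are split into two arms. Section 4 says "The Tdh and Cesvi collaborators then selected 26 facilities per country" and Section 6.2 says "13 schools are needed per arm with 50 students per school". The Synopsis, by contrast, says "This will lead to 26 schools in total with a total number of 1300 students". The Synopsis also says of the absence diary: "Module 4 data collection will take place in both study arms longitudinally starting after the intervention has been implemented". Under Module 4, Section 4 lists six hygiene-related conditions, which Section 4.2 leaves open to reassessment.

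The rule itself does not state whether the average is per country or over both, whether conditions are pooled or taken singly, or what period is covered.

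**The concern.** A trigger of this kind should notice harm that the trial itself might cause, and such harm would tend to appear in many intervention schools at once. The protocol acknowledges one possible route. The water-recycling handwashing station is part of the intervention in Nigeria only (Section 2.3), and Section 9.2 says: "Health effects of regular ingestion of Gravit'eau water have so far not been tested".

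With intervention schools in the benchmark, a shared rise is compared partly with itself. The diary starts after implementation, so it holds no earlier level for a school that could serve instead. The randomised control schools are the natural comparator, and the rule mixes them with the schools being watched. The benchmark can also err the other way: if the intervention lowers illness, control schools move above the average without any excess.

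**Working it through.** **Allocation.** For 20% against 45%, the usual pooled-variance formula gives 54 pupils per arm. The design effect is 1 + 49 × 0.2 = 10.8, and 54 × 10.8 / 50 = 11.7 schools. A t-based power calculation gives 79.7% at 12 schools and 83% at 13, so the plan's 13 per arm is reproduced. The intervention share of the benchmark is therefore one half. The 25% line is a set value with no derivation to check.

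**Shared rise, expected rates.** Suppose a fraction f of the averaged schools has relative rate R and the rest have rate 1. An affected school's ratio to the average is R / (1 − f + fR). Setting this to 1.25 gives R = 1.25(1 − f) / (1 − 1.25f).

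- f = 1/2 (13 of 26, or 26 of 52): R = 0.625 / 0.375 = 1.667, so +67%. A shared +25% reads as 1.11, +50% as 1.20 and a doubling as 1.33.
- f = 1/4 (Nigeria's 13 intervention schools among 52): R = 0.9375 / 0.6875 = 1.364, so +36%.
- f = 1/26 (one school alone): R = 1.263, so about +26%. For an isolated problem the line works as intended.
- Against the control-school average, the line is reached at R = 1.25 in every case.

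**Allowing for chance.** The documents give no event counts. The simulation assumes Poisson counts, conditions pooled, one check, and 13 + 13 schools in one country. The table gives the share of intervention schools referred, as written and then with the control comparison added.

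| Assumed events per school | No effect | Shared +50% | Shared doubling |
|---|---|---|---|
| 30 | 9% → 11% | 38% → 86% | 68% → 100% |
| 60 | 3% → 4% | 34% → 94% | 76% → 100% |
| 120 | 0.3% → 0.6% | 28% → 99% | 84% → 100% |

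At 60 events and a shared +50%, 34% is 4.4 of 13 schools. As written, more data make referral at +50% less likely, because the expected ratio of 1.20 lies below the line. If 52 schools are pooled and only Nigeria's arm rises by 50%, 72% of affected schools are referred as written.

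**Country scope.** If countries are pooled and one has r times the illness of the other, its typical school stands at 2r / (1 + r). This passes 1.25 once r exceeds 1.67, with no excess in any school.

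**Pooling of conditions.** Suppose only diarrhoea rises, it is one sixth of all episodes (assumed), and conditions are pooled. With x = (R − 1)/6, solving (1 + x) / (1 + x/2) = 1.25 gives x = 0.667 and R = 5.0. Against control schools, R = 1 + 0.25 × 6 = 2.5.

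**Control schools.** Section 2.1.1 cites a 30% to 48% reduction in diarrhoea from handwashing with soap. Assume that this applies to pupils who wash, at the planned 20% and 45% uptake.

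- At 30%: control 1 − 0.30 × 0.20 = 0.940, intervention 1 − 0.30 × 0.45 = 0.865, a fall of 8.0%.
- At 48%: control 0.904, intervention 0.784, a fall of 13.3%.
- A typical control school stands at 2 / (2 − fall): 2 / 1.920 = 1.04 and 2 / 1.867 = 1.07, so 4% to 7% above average.

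**The case against.** A reader might infer that no shared rise below 67% would ever be noticed. The documents do not support that. The rule acts school by school, and under the 60-event, one-country assumption at least one intervention school is referred in 99.9% of runs at a shared +50%. Field staff and the statistician are unblinded (Section 4.3), so a one-sided cluster of referrals could be seen. The 67% also depends on scope: a literal reading of all schools may pool both countries, and the figure for Nigeria's arm alone is then 36%. Both points stand and limit the claim. They do not remove the dilution, and nothing in the rule directs anyone to look across referrals by arm.

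A reader might also apply the cited 30% to 48% to the whole arm and conclude that control schools would stand 18% to 32% above average. That treats an effect of handwashing itself as if uptake went from none to all. At the planned contrast the shift is modest.

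The named hazard has direct controls. Section 4.3 sets integrity and *E. coli* tests with remedial action, and Section 9.2 provides labels saying that the water is not for drinking. These are real safeguards, but they check the water and warn pupils; they do not track illness. The conditions are listed under Module 4, so only how they are counted is open. Finally, the diary is teacher-reported and exploratory, and no efficacy conclusion rests on this rule.

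**Conclusion.** The point holds as a weakness in safety monitoring, worth correcting but not critical. The break-even for a rise shared by the intervention arm is +67% per country (or with both intervention arms affected) and +36% if 52 schools are pooled and only Nigeria's arm is affected. In either case it is above the nominal 25%. These are expected-rate figures that assume equal arms and equal underlying illness. With chance included, a shared +50% in one country would refer about 4 of 13 schools at 60 assumed events and leave most affected schools unreferred. The ministries can filter the referrals they receive but cannot act on schools that are not referred. Over-referral of control schools is a secondary issue, at about 4% to 7% above average for diarrhoea if the cited effect carries over to the planned uptake. Event counts are assumed throughout the simulation; the direction was the same from 30 to 120 events per school.

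**What to change.** In Section 4.3, replace the condition that opens the rule with wording such as: 'At each quarterly diary review, episodes per 100 student-weeks since the start are compared within each country. An intervention school is referred to the ministries if its rate exceeds the all-school average, or the control-school average, by more than 25%. A control school is referred if its rate exceeds the control-school average by more than 25%.' State whether the Module 4 conditions are counted together, singly or both. The 25% line, the ministry consultation and the stop rule stay unchanged, as do the water tests and the labels.

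The change uses diary rates and a quarterly look that are already planned. Intervention schools lose no sensitivity, because the existing comparison is kept. There are two costs:

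- Referrals of unaffected intervention schools rise from about 3% to 4% at 60 assumed events and one check, and from 20% to 25% over four cumulative checks.
- If unblinded intervention teachers record 20% more illness with no true excess (assumed), referrals rise from 11% to 36% of intervention schools. The ministry consultation would have to filter these, and it would help to give the ministries the per-condition rates.
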